10.3.3. Definition of AESI

The following types of AEs are considered AESIs:

- All infections: viral, fungal, bacterial
- Acute mononucleosis-like illness (eg, fever, pharyngitis, lymphadenopathy)
- CMV viremia defined using DNA PCR testing and >10,000 copies per mL serum or 10⁶ cells
- EBV viremia defined using DNA PCR testing and >10,000 copies per mL serum or 10⁶ cells
- Herpes zoster or other conditions related to VZV
- Primary infection with or reactivation of latent tuberculosis
- Infections requiring IV antibiotic treatment
- Demyelinating diseases
- Malignancies including lymphomas
- Severe hypoglycemic episodes that require assistance by another individual through the administration of oral or parenteral dextrose, glucagon or intervention
- ≥ Grade 3 liver function abnormalities (AST, ALT, bilirubin)
- ≥ Grade 3 thrombocytopenia (platelet counts less than 50,000/µL)
- ≥ Grade 3 allergic/hypersensitivity reaction (anaphylaxis)
- ≥ Grade 3 Rash

- \geq Grade 3 cytokine-release syndrome
- \geq Grade 4 neutropenia (<500 PMN/ μ L on 2 consecutive evaluations performed on different days)

10.3.4. Reporting and Follow-Up of AE and/or SAE

AE and SAE Reporting

Timely, accurate, and complete reporting and analysis of safety information from clinical studies are crucial for the protection of participants, Investigators, and the Sponsor, and are mandated by regulatory agencies worldwide. The Sponsor has established Standard Operating Procedures in conformity with regulatory requirements worldwide to ensure appropriate reporting of safety information; all clinical studies conducted by the Sponsor or its affiliates will be conducted in accordance with those procedures.

The determination of seriousness, severity and causality must be made by the physician Investigator who is qualified to review adverse event information, provide a medical evaluation of adverse events, and classify adverse events based upon medical judgment.

An adverse event is any untoward medical occurrence in a clinical study participant from the time they formally agree to participate in the study (eg, by providing informed consent/assent) through their last study contact (eg, last visit or status update). An adverse event does not necessarily have a causal relationship with the study drug. An adverse event can therefore be any unfavorable and unintended sign (including an abnormal finding), symptom, or disease temporally associated with the use of a study drug (investigational or non-investigational product), whether or not related to that study drug (investigational or non-investigational product).

This includes any occurrence that is new in onset or aggravated in severity or frequency from the baseline condition, or abnormal results of diagnostic procedures, including laboratory test abnormalities.

A treatment-emergent adverse event (TEAE) is defined as an AE that occurs after the first dose of study drug administration (Day 1) through the end of the study or early termination.

The Investigator must follow all SAEs (including serious AESIs) until resolution even if this extends beyond the study-reporting period. Resolution of a SAE is defined as the return to pre-treatment status or stabilization of the condition with the expectation that it will remain chronic. At any time after completion of the study, if an Investigator becomes aware of a serious adverse event that s/he suspects is related to study drug, the Investigator should report the event to the Pharmacovigilance contact.

These events will be captured on the CRF and reported to the Sponsor as described in Section 8.4.1.1. Any event that meets serious adverse event criteria will be reported to the Sponsor within the appropriate timeline as described in Section 8.4.1.4.

Events will be assessed and reported consistent with the ICH Guideline for Good Clinical Practice and per the guidance of the DHHS Office for Human Research Protections (OHRP).

Event outcome and other follow-up information regarding the treatment and resolution of the event will be obtained and reported when available, if not known at the time the event is initially reported. The follow-up information should contain sufficient detail to allow for a complete medical assessment of the case and an independent determination of possible causality.

AESIs should be reported according to the requirements for SAEs.

Assessment of Severity

An assessment of severity grade for each AE will be made by the site Investigator according to the criteria set forth in the National Cancer Institute's Common Terminology Criteria for Adverse Events Version 5.0. This document (referred to herein as the "CTCAE V5.0") provides a common language to describe levels of severity, to analyze and interpret data, and to articulate the clinical significance of all AEs. The Investigator should use clinical judgment in assessing the severity of events not directly experienced by the participant (eg, laboratory abnormalities).

Adverse events will be graded according to National Cancer Institute (NCI) Common Terminology Criteria for Adverse Events (CTCAE) version 5.0:

- Grade 1 = Mild adverse event.
- Grade 2 = Moderate adverse event.
- Grade 3 = Severe adverse event.
- Grade 4 = Life-threatening or disabling adverse event.
- Grade 5 = Death

Assessment of Causality

The Investigator is required to provide an assessment of causality or relationship of adverse events to the study drug based on 1) temporal relationship of the event to the administration of study drug; 2) whether an alternative etiology has been identified; and 3) biological plausibility. The causality assessment categories that will be used for this study are described below.

Causality assessments considered **not** related to study drug:

- Unrelated: The event is related to an etiology other than the study drug (the alternative etiology must be documented in the participant's medical record).
- Unlikely: The event is unlikely to be related to the study drug and likely to be related to factors other than study drug.

Causality assessments considered **related** to study drug:

- Possible: There is an association between the event and the administration of the study drug and there is a plausible mechanism for the event to be related to study drug; but there may also be alternative etiology, such as characteristics of the participant's clinical status or underlying disease.
- Probable: There is an association between the event and the administration of study drug, a plausible mechanism for the event to be related to the study drug and the event could not be reasonably explained by known characteristics of the participant's clinical status or an alternative etiology is not apparent.

Definite: There is an association between the event and the administration of study drug, a plausible mechanism for the event to be related to the study drug and causes other than the study drug have been ruled out and/or the event re-appeared on re-exposure to the study drug.

10.4. Appendix 4: Contraceptive Guidance and Collection of Pregnancy Information

Definitions:

Woman of Childbearing Potential (WOCBP)

A woman is considered fertile following menarche and until becoming post-menopausal unless permanently sterile (see below).

If fertility is unclear (e.g., amenorrhea in adolescents or athletes) and a menstrual cycle cannot be confirmed before first dose of study intervention, additional evaluation should be considered.

Women in the following categories are not considered WOCBP

1. Premenarchal
2. Premenopausal female with 1 of the following:
 - Documented hysterectomy
 - Documented bilateral salpingectomy
 - Documented bilateral oophorectomy

For individuals with permanent infertility due to an alternate medical cause other than the above, (e.g., mullerian agenesis, androgen insensitivity), investigator discretion should be applied to determining study entry.

Note: Documentation can come from the site personnel's: review of the participant's medical records, medical examination, or medical history interview.

3. Postmenopausal female:

- A postmenopausal state is defined as no menses for 12 months without an alternative medical cause.
 - A high follicle stimulating hormone (FSH) level in the postmenopausal range may be used to confirm a postmenopausal state in women not using hormonal contraception or hormonal replacement therapy (HRT). However, in the absence of 12 months of amenorrhea, confirmation with more than one FSH measurement [insert threshold if required (>40 IU/L or mIU/mL) or remove to allow for flexibility with different local thresholds for defining postmenopausal state] is required.
- Females on HRT and whose menopausal status is in doubt will be required to use one of the non-estrogen hormonal highly effective contraception methods if they wish to continue their HRT during the study. Otherwise, they must discontinue HRT to allow confirmation of postmenopausal status before study enrollment.

Male participants with partners who become pregnant

- The investigator will attempt to collect pregnancy information on any male participant's female partner who becomes pregnant while the male participant is in this study. This applies only to male participants who receive [study intervention].

- After obtaining the necessary signed informed consent from the pregnant female partner directly, the investigator will record pregnancy information on the appropriate form and submit it to the sponsor within [24 hours] of learning of the partner's pregnancy. The female partner will also be followed to determine the outcome of the pregnancy. Information on the status of the mother and child will be forwarded to the sponsor. Generally, the follow-up will be no longer than 6 to 8 weeks following the estimated delivery date. Any termination of the pregnancy will be reported regardless of fetal status (presence or absence of anomalies) or indication for the procedure.

Female Participants who become pregnant

- The investigator will collect pregnancy information on any female participant who becomes pregnant while participating in this study. The initial information will be recorded on the appropriate form and submitted to the sponsor within [24 hours] of learning of a participant's pregnancy.
- The participant will be followed to determine the outcome of the pregnancy. The investigator will collect follow-up information on the participant and the neonate and the information will be forwarded to the sponsor. Generally, follow-up will not be required for longer than 6 to 8 weeks beyond the estimated delivery date. Any termination of pregnancy will be reported, regardless of fetal status (presence or absence of anomalies) or indication for the procedure.
- While pregnancy itself is not considered to be an AE or SAE, any pregnancy complication or elective termination of a pregnancy for medical reasons will be reported as an AE or SAE.
- A spontaneous abortion (occurring at <22 weeks gestational age) or still birth (occurring at >22 weeks gestational age) is always considered to be an SAE and will be reported as such.
- Any post-study pregnancy related SAE considered reasonably related to the study intervention by the investigator will be reported to the sponsor. While the investigator is not obligated to actively seek this information in former study participants, he or she may learn of an SAE through spontaneous reporting.
- Any female participant who becomes pregnant while participating in the study [will discontinue study intervention or be withdrawn from the study] OR [may request continuation of study intervention].

10.5. Appendix 5: Abbreviations

ADA	American Diabetes Association
AE	adverse event
AESI	adverse event of special interest
ALT	alanine aminotransferase
AST	aspartate aminotransferase
AUC	area under the time-versus-concentration curve
BP	blood pressure
BSA	body surface area
BUN	blood urea nitrogen
CBC	complete blood count
CD	cluster of differentiation
CMV	cytomegalovirus
CRF	case report form(s) (paper or electronic as appropriate for this study)
CRS	cytokine-release syndrome
CTCAE	Common Terminology Criteria for Adverse Events
DCCT	Diabetes Control and Complications Trial
DKA	diabetic ketoacidosis
DNA	deoxyribonucleic acid
DPT-1	Diabetes Prevention Trial – Type 1
EBNA	Epstein Barr nuclear antigen
EBV	Epstein-Barr virus
EDC	electronic data capture
ENDIT	European Nicotinamide Diabetes Intervention Trial
ET	early termination
Fc	fragment crystallizable region of an antibody/immunoglobulin molecule
FcR	receptor binding to the Fc component of antibody molecules
FDA	Food and Drug Administration
GCP	Good Clinical Practice
HbA1c	hemoglobin A1c
HBV	hepatitis B virus
HCV	hepatitis C virus
HIV	human immunodeficiency virus
HR	heart rate
IB	Investigator Brochure
ICF	informed consent form

ICH	International Council for Harmonisation
IEC	Independent Ethics Committee
Ig	immunoglobulin
IGRA	interferon gamma release assay
IHSG	International Hypoglycaemia Study Group
IL	interleukin
IRB	Institutional Review Board
ITT	intent to treat
IV	intravenous(ly)
KD	kilodalton
LDH	lactate dehydrogenase
LFT	liver function test
mAb	monoclonal antibody
MedDRA	Medical Dictionary for Regulatory Activities
MHC	major histocompatibility complex
MMTT	mixed meal tolerance test
NAb	neutralizing antibody
NCI	National Cancer Institute
NSAID	nonsteroidal anti-inflammatory drug
PBMC	peripheral blood mononuclear cell
PCR	polymerase chain reaction
PK	pharmacokinetic(s)
PMN	polymorphonuclear leukocyte
PPD	purified protein derivative
PVC	polyvinyl chloride
RNA	ribonucleic acid
RR	respiratory rate
SAE	serious adverse event
SAP	Statistical Analysis Plan
SD	standard deviation
SUSAR	suspected unexpected serious adverse reaction
TEAE	treatment-emergent adverse event
T1D	type 1 diabetes
TN-10	Anti-CD3 Monoclonal Antibody (Teplizumab) for Prevention of Diabetes in Relatives At-Risk for Type 1 Diabetes Mellitus Trial
TB	tuberculosis
TCR	T cell receptor

TEAE	treatment-emergent adverse event
U	unit
ULN	upper limit of normal range
VZV	varicella zoster virus
WBC	white blood cell
ZnT8	zinc transporter 8

11. References

1 INTRODUCTION

This is a statistical analysis plan (SAP) for study PRV-031-002 which is based on the final study protocol version 1.0 (dated 02DEC2019). This SAP describes the statistical analyses which will be presented in the clinical study report.

The SAP is a supplement to the study protocol, which should be referred to for additional details on study objectives, endpoints, study design, study conduct, and other operational aspects of the study.

2 STUDY OBJECTIVES AND ENDPOINTS

Objectives and Endpoints

Objectives	Endpoints
Primary	

 To evaluate the safety and tolerability of teplizumab treatment, administered intravenously (IV) to participants in the TN-10 trial who have developed T1D. 	
 Incidence of treatment-emergent adverse events (TEAEs), adverse events of special interest (AESIs), and serious adverse events (SAEs)
Secondary	

 To evaluate the pharmacokinetics (PK) and immunogenicity of teplizumab 	
 Levels of teplizumab in the serum and anti-drug antibodies

 To evaluate whether teplizumab treatment reduces the loss of β cells, over 78 weeks (18 months), in individuals with recent diagnosis of T1D. 	
 The area under the time-versus-concentration curve (AUC) of C-peptide after a 4-hour (4h) mixed-meal tolerance test (MMTT), a measure of endogenous insulin production and β cell function, over 78 weeks

 To evaluate key clinical parameters of diabetes management, including insulin use, hemoglobin A1c (HbA1c), and clinically important hypoglycemic episodes over 78 weeks 	
 HbA1c levels; insulin use, defined as a daily average dose in units per kilogram per day (U/kg/day); and frequency of clinically important hypoglycemic episodes over 78 weeks

 To evaluate whether treatment with teplizumab increases the frequency of exhausted T cells 	
 Frequency of CD8+ TIGIT+ KLRG1+ T cells

3 STUDY TYPE AND DESIGN

This is a single-arm, multi-center, open-label clinical trial. Teplizumab-treated and placebo participants from the TN-10 trial who develop clinical type 1 diabetes after the conclusion of that trial, are eligible to enroll and receive teplizumab treatment in this open-label study within one year of Stage 3 clinical T1D diagnosis.

[figure not shown]
Up to 30 participants may be enrolled in this study.

All participants will receive a 12-day course of teplizumab given through a daily IV infusion. The participant's dosing course will be based on the body surface area (BSA), in m^2 , calculated on Study Day 1. The drug dosing is as follows:

- Day 1: $106 \mu\text{g}/\text{m}^2$
- Day 2: $425 \mu\text{g}/\text{m}^2$
- Days 3-12: $850 \mu\text{g}/\text{m}^2$

Participants will have a screening period of up to 4 weeks, a treatment period of 12 days, and a follow-up period of up to 78 weeks (18 months) from the first dose of treatment. The study schema is shown in [Figure 1](#).

Figure 1 Study Schema

4 RANDOMIZATION

Randomization is not applicable for this open-label study.

5 STATISTICAL HYPOTHESES

There is no formal statistical hypothesis to be tested in this study. The primary objective is to evaluate the safety of teplizumab administration in participants of the TN-10 trial who have developed clinical T1D. For the secondary endpoints, it is proposed that teplizumab treatment will reduce the loss of beta cell function (as measured by C-peptide) and will increase the frequency of exhausted T cells, TIGIT + KLRG1 + CD8 + T cells, compared to baseline (at the start of study drug administration).

6 ESTIMATION OF SAMPLE SIZE

Sample size calculation was not based upon any formal statistical considerations. The sample size will include a maximum of 30 participants who develop clinical T1D after the conclusion of the TN-10 trial.

7 STATISTICAL METHODS

7.1 Analysis sets

The Enrolled analysis set will be comprised of all participants who sign the informed consent and/or assent.

The Safety analysis set will be comprised of all participants who receive at least one dose of the study drug.

The PK analysis set will be comprised of participants from the Safety analysis set who have at least one evaluable sample for PK analysis.

The Immunogenicity analysis set will be comprised of participants from the Safety analysis set who have at least one evaluable sample for Immunogenicity analysis.

7.2 General statistical considerations

No inferential statistical analysis will be performed. Only descriptive statistics will be presented. Data listings will provide both the participant identification number and treatment arm from the TN-10 trial as well as the participant identifier in the TN-10 Extension study. Summary tables will, in general, have a Total column only; however, where noted, tables will be presented by prior treatment (teplizumab or placebo) in the parent TN-10 trial.

Continuous variables and the respective changes from baseline (if applicable) will be summarized by assessment time using the number of observations (n), mean, standard deviation (SD), median and minimum and maximum. Unless otherwise specified, categorical variables will be presented by the number of participants and percentages based on the respective analysis set.

Decimal places for summary statistics are given in [Table 2](#). For derived variables such as BMI, value should be rounded to 1 decimal place and the same rules should be applied as in [Table 1](#).

Table 1 Decimal places for summary statistics of continuous variables

Statistic	Number of digits
Minimum, maximum	Same as original data
Mean, median	1 more than in original data
SD	2 more than in original data
Frequencies (%)	1 decimal place

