Lymphomas or other malignancies	SOC – 'Neoplasms benign, malignant and unspecified (incl cysts and polyps)' and HLT – includes 'malignant' or 'lymphomas' or 'benign'

Severe hypoglycemic episodes	PT – 'Hypoglycaemic seizure', 'Hypoglycaemic coma', 'Hypoglycaemic unconsciousness' of any grade; PT – 'Hypoglycaemia' of ≥ Grade 3
≥ Grade 3 liver function abnormalities (aspartate aminotransferase [AST], alanine aminotransferase [ALT], bilirubin) i.e., an AST or ALT value >5.0x upper limit of normal (ULN) or a bilirubin value >3.0x ULN	PT – 'Alanine aminotransferase increased', 'Aspartate aminotransferase increased', 'Blood bilirubin increased', 'Liver function tests increased', 'Hypertransaminasemia', 'Transaminase elevation', 'Hyperbilirubinemia'; ≥ Grade 3
≥ Grade 3 thrombocytopenia (platelet counts less than 50,000/µL)	PT – 'Thrombocytopenia'; ≥ Grade 3
≥ Grade 3 neutropenia (<1000 polymorphonuclear leukocytes [PMN]/µL) on 2 consecutive evaluations performed on different days	PT – 'Neutropenia'; ≥ Grade 3
≥ Grade 4 allergic/hypersensitivity reaction, i.e., anaphylaxis	PT – 'Dermatitis allergic', 'Drug hypersensitivity', 'Anaphylactic reaction', 'Immune reaction', 'Anaphylaxis', 'Hypersensitivity', 'Infusion related reaction', 'Serum sickness'; ≥ Grade 4
≥ Grade 3 rash	SOC – 'Skin and subcutaneous tissue disorders'; ≥ Grade 3
≥ Grade 4 cytokine-release syndrome, i.e., life-threatening; pressor or ventilatory support indicated	PT – 'Cytokine release syndrome'; ≥ Grade 4
Lymphocyte count <500 mm ³ for 7 days or longer	PT – 'Lymphopenia'; ≥ Grade 3; at least 7 days

SOC = system organ class; PT = preferred term; HLT = high level term

Note: Nasopharyngitis, Pharyngitis, pharyngitis streptococcal should not be included in search criteria.

Summary Tables

An overall summary table of treatment emergent adverse events will display the number and percentage of participants with at least one

- TEAE
- TEAE related to study treatment
- TEAE leading to study treatment discontinuation
- TEAE leading to study discontinuation
- TEAE leading to death
- TEAE by CTCAE grade
- TEAE of special interest (AESI)
- Serious TEAE
- Serious TEAE related to study treatment

Summary tables will be produced which display the number and percentage of participants having at least one of the following categories by MedDRA System Organ Class (SOC) and Preferred Term (PT):

- TEAE
- TEAE related to study treatment
- TEAE leading to study treatment discontinuation

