- TEAE leading to study discontinuation
- Serious TEAE
- Serious TEAE related to study treatment

Summary tables will be produced by descending frequency of MedDRA Preferred Term (PT) for the following categories:

- TEAE

A summary table will be produced by AESI category (defined in [Table 2](#)) and MedDRA Preferred Term for the following category:

- TEAE of special interest (AESI)

Participants with more than one TEAE in each SOC or PT will only be represented once per row in these summary tables by SOC and/or PT.

Data Listings

The following data listings for adverse events will be produced:

- TEAE
- Adverse events which are not treatment emergent
- TEAE leading to study treatment discontinuation
- TEAE leading to study discontinuation
- TEAE leading to death
- TEAE of special interest (AESI)
- Serious TEAE

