7.8 Other analyses

7.8.1 Mixed Meal Tolerance Test (MMTT)

The area under the time-versus-concentration curve (AUC) of C-peptide after a 4-hour MMTT will be calculated using the trapezoidal rule. To adjust the potential different durations of the MMTT test, C-peptide AUC will first be standardized by the duration of the MMTT test for the analysis. If the C-peptide values at time -10 minutes and time 0 minutes are missing, the AUC will be set to missing for the MMTT. If fewer than two measurements are available to calculate the AUC for a MMTT, the AUC will be set to missing.

A summary table will provide descriptive statistics of the C-peptide $\ln(\text{AUC}+1)$ by visit and by prior treatment in the TN-10 trial. As historical data have shown the C-peptide AUC is right skewed, the $\ln(\text{AUC}+1)$ transformation will be applied before summarization.

The values of the MMTT results, including both untransformed and transformed AUC, will be presented in a data listing.

Graphical presentation of the $\ln(\text{AUC}+1)$ over time may be explored.

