7.8.2 HbA1c (%)

A summary table will provide descriptive statistics of HbA1c (%) by visit and by prior treatment in the TN-10 trial.

A data listing will be provided displaying results of local HbA1c (%) testing.

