7.8.3 Exogenous Insulin

Exogenous average daily insulin use (unit/kg/day) in the TN-10 Extension study will be presented by visit and prior treatment in the TN-10 trial.

The average daily insulin use for a particular visit will be derived based on the 3 days of insulin recorded in the case report form prior to a visit. The body weight (kg) at the visit, if available, will be used in the calculation; otherwise, the average of the closest prior and post-visit weights will be used.

Information on exogenous insulin will be presented in a data listing. The listing will include the nominal day reported (3 days prior to visit, 2 days prior to visit, 1 day prior to visit) as well as the insulin name and dosing.

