7.8.4 Insulin Discontinuation Criteria

TN-10 Extension participants meeting insulin discontinuation criteria (defined as $\text{HbA1c} \leq 6.5\%$ and average daily insulin use ≤ 0.25 unit/kg/day) at each visit will be summarized, by prior TN-10 trial

treatment and overall. Only participants who have available HbA1c and insulin data at the relevant visit will be included in the summary.

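### No adverse event table in SAP 7.7.1 is noted as split by prior TN-10 treatment, although SAP 7.8.1 to 7.8.4 split four other outcomes that way: a cheap improvement, not an error

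*SAP*

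**What the plan says.** The layout rule is in SAP 7.2: "Summary tables will, in general, have a Total column only; however, where noted, tables will be presented by prior treatment (teplizumab or placebo") in TN-10. The same section provides for the listings: "Data listings will provide both the participant identification number and treatment arm from the TN-10 trial".

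SAP 7.7.1 then specifies the adverse event tables. The first is the overall one: "An overall summary table of treatment emergent adverse events will display the number and percentage of participants with at least one" of a list of items that includes any TEAE, any AESI and any serious TEAE. Next come tables by system organ class and preferred term, and a table by descending preferred-term frequency. For events of special interest, "A summary table will be produced by AESI category" and preferred term. None of these is noted as split by prior treatment.

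Four later sections do note a split:

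- SAP 7.8.1, C-peptide: "by visit and by prior treatment in the TN-10 trial".
- SAP 7.8.2, HbA1c: "A summary table will provide descriptive statistics of HbA1c (%) by visit and by prior treatment in the TN-10 trial".
- SAP 7.8.3, average daily insulin: "will be presented by visit and prior treatment in the TN-10 trial".
- SAP 7.8.4, insulin-discontinuation criteria: "at each visit will be summarized, by prior TN-10 trial" treatment, and also overall.

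SAP 7.6 tabulates whether each participant had teplizumab in TN-10 and how long ago, but does not set this against events. SAP 7.10, which lists departures from the protocol, is silent on the layout of the safety tables.

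**The concern.** Incidence of TEAEs, AESIs and SAEs is the primary endpoint. The trial treats two kinds of participant: those who had placebo in TN-10 and meet teplizumab for the first time, and those who had teplizumab in TN-10 and are re-exposed. Protocol 4.2 says that second courses have not produced more adverse events than first courses. It also says that the gap between courses here exceeds what has been studied; Protocol 4.3 describes earlier two-course designs with gaps of 6 or 12 months.

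A pooled column cannot show which kind of participant had the events. The report would therefore have no table giving incidence after re-exposure at this longer interval, although four other outcomes are shown by prior treatment in the same small groups.

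**Working it through.** **Text check.** I compared each adverse event table in SAP 7.7.1 with the 7.2 rule.

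| Section | Content | Split by prior treatment noted? |
|---|---|---|
| 7.7.1 | Overall TEAE summary | No |
| 7.7.1 | SOC/PT tables | No |
| 7.7.1 | PT by descending frequency | No |
| 7.7.1 | AESI category by PT | No |
| 7.8.1 | C-peptide | Yes |
| 7.8.2 | HbA1c | Yes |
| 7.8.3 | Insulin use | Yes |
| 7.8.4 | Insulin-discontinuation criteria | Yes, plus overall |

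Total only for 7.7.1 is inferred from the 7.2 default and the absence of any note; 7.7.1 does not itself say so.

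**Group ceilings.** The plan states no figure for the two groups, so there is none to reproduce. Protocol 2.2.1 gives 44 teplizumab and 32 placebo participants, with 19 and 23 diagnosed in TN-10. Protocol 5.1 requires diagnosis after TN-10 ended. At most:

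- prior teplizumab: 44 − 19 = 25
- prior placebo: 32 − 23 = 9
- together: 34

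Protocol 9.2 says 33. Either reading of that (24 + 9 or 25 + 8) stays within the two ceilings.

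**At the cap of 30 (SAP 6).**

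- Prior placebo is at most 9, so prior teplizumab is at least 30 − 9 = 21 (21/30 = 70.0%).
- Prior teplizumab is at most 25 (25/30 = 83.3%), so prior placebo is at least 30 − 25 = 5.

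**Below the cap.** With N enrolled, prior teplizumab is at least N − 9. It must be the larger group only when N − 9 > 9, that is N ≥ 19. At N = 18 a 9:9 split is possible, and at N ≤ 17 either group could be the larger. Reaching 30 would take 30/34 = 88.2% of the whole pool.

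**What pooling hides (illustration; the 3 participants with an event and full enrolment are assumptions).** A Total of 3/30 = 10.0% is the same in both of these cases:

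- 3/21 = 14.3% re-exposed and 0/9 first-time
- 0/21 re-exposed and 3/9 = 33.3% first-time

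**What the split could support.** With zero events in n participants, the exact two-sided 95% upper limit is 1 − 0.025^(1/n).

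| n | Upper limit |
|---|---|
| 30 | 11.6% |
| 25 | 13.7% |
| 21 | 16.1% |
| 9 | 33.6% |
| 5 | 52.2% |

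Smaller groups give wider limits.

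**The case against.** The strongest case is that this is a layout preference. The trial is single-arm and descriptive, its safety objective treats TN-10 participants who developed T1D as one population, and Protocol 9.4.1 promises descriptive presentation and leaves detail to the SAP. The arm is in the listings, which cover TEAEs, AESIs, serious TEAEs and deaths, and SAP 7.6 adds a per-participant exposure listing across both trials. Reliance on listings was deliberate: the document history attributes it to expected enrolment, and SAP 7.10 drops the historical C-peptide comparison because few were enrolled. All of this stands, and it rules out calling the omission an error or a breach of the protocol.

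Small numbers alone do not explain the difference, however. The SAP accepts the same groups in 7.8.1 to 7.8.4, and it does plan adverse event tables; only their columns are at issue.

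A reader might also infer that Protocol 4.2 promises a safety comparison with prior-placebo participants. It does not. It names them as comparator for immunologic effects, ties the uncertainty about the interval to anti-drug antibodies, and reports no identified safety concern. Extending that uncertainty to adverse events is my inference.

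Nor would the columns test the protocol's statement about second courses. They set second courses in some people beside first courses in others. These groups are no longer randomised: each is selected on staying free of T1D through TN-10 and being diagnosed later, after different TN-10 treatment.

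**Conclusion.** The gap is real and modest. As written, the primary endpoint tables do not separate first-time from re-exposed participants, so incidence after re-exposure has to be counted by hand from listings. This rests on reading silence in 7.7.1 as the 7.2 default.

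It is tempting to add that the Total would mostly describe re-exposed participants. The documents support that only conditionally: the 70.0% to 83.3% range holds if enrolment reaches 30, and a re-exposed majority is certain only from 19 upwards. The actual number and split are not given, and the SAP's own remarks point to small enrolment. What holds at any enrolment is the pair of ceilings, 25 and 9.

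The change should be made because it is nearly free and makes the primary endpoint readable by exposure history. It would not support a conclusion about the relative safety of a second course.

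**What to change.** In SAP 7.7.1, state that two tables have columns for prior teplizumab, prior placebo and Total: the overall TEAE summary (including the any-AESI and any-serious-TEAE rows) and the AESI-category table. Show counts as n/N, label the split descriptive, and add a footnote that the groups are not a randomised comparison. The SOC/PT and descending-PT tables may stay Total only.

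The cost is one sentence and two table shells. Prior arm is already in the listings and the exposure table, and 7.8.4 already uses the layout of prior treatment plus overall. The downside is very small cells whose percentages could be over-read, which is the reason for the n/N display and the footnote.
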